Official Title : Effects of low-dose corticosteroids on survival of severe community-acquired pneumonia

| | |
|--|---|
| 
MAJOR CHANGES IN THE ORIGINAL PROTOCOL – DESIGNS ISSUES
 | 
Methodological issues are the following:
 
 - Cape-COVID is planned as a group sequential randomized trial - The primary outcome is different as the one of the original trial. We will now consider failure at Day 21 were failure corresponds to death or dependence from respiratory support, including mechanical ventilation or high-flow oxygen therapy. This outcome makes sense at both individual and community levels. Indeed, prolongation of respiratory support, especially mechanical ventilation, is associated with several complications (e.g. ventilator-associated pneumonia, ventilator-induced lung injury, acquired muscle weakness or sleep deprivation) and increase ICU stay. Moreover, in the context of rapidly progressive pandemic with a risk of exceeding critical care capacities, diminishing the duration of respiratory support will permit to decrease ICU length-of-stay and to liberate ICU-beds for other patients. This beneficial effect of CTx is consistent with previous studies in non-severe community-acquired pneumonia who have shown that CTx decrease the time for clinical stability and hospital length-of-stay. - The sample size has been calculated with an assumption on the failure rate associated to the control group which is no well documented. We will therefore allow ourselves to revise this sample size while the trial is going on - Therapeutic units will be those we planned to use for the original trial. However, we presently have about 290 therapeutic units, knowing that about 50 COVID19 patients have already been included. It is presently impossible to obtain new placebo units. As a consequence, the trial is planned as being blinded, but in case we need to include more patients than we have units, we plan to end the trial as an open trial. |
| 
SAMPLE SIZE
 | 
The event rate is assumed to be 30% in the control group. The trial is designed to demonstrate superiority of experimental treatment over control with an assumed event rate of 15% in the experimental group with 80% power and a one-sided Type I error rate of 2.5. Symmetric two-sided group sequential, requires sample size 290, for 6 interim analyses (5 during the trial and one final). Bounds were determined using a Kim-DeMets alpha spending function (Lan et al, Biometrika 1983;70:659-63; kim et al Biometrics 1987;4:857-64; DeMets et al Statist Medicine 1994;13:1341-52) with a conservative bound for efficacy and an aggressive bound for futility. That is, stopping for high
 |

| | |
|----------------------|--|
| | 
evidence of superiority while stopping early if the experimental treatment is not effective and can be potentially harmful for patients.
 
Due to uncertainty of the failure rate in the control group, we plan to re-calculate this sample size while the trial is going-on. Indeed, data about mortality rate of COVID patients in ICU are diverging and ranging from 50% to 5%. We choose to assume a 30% rate considering mortality or need of respiratory support for the control arm but this is uncertain. This is why sample size re-estimation could be necessary during the trial when up-dated knowledge will be available.
 |
| STATISTICAL ANALYSIS | 
The statistical design for this phase III two arms clinical trial will follow a group sequential design with a total of 6 analyses (5 interim analyses and a final). The group sequential will use a Kim-DeMets alpha spending function with a conservative bound for efficacy and an aggressive bound for futility. That is, a conservative O'Brien Fleming type of bound for superiority bound and a an aggressive bound for futility design. The alpha spending function has the advantage to be a continuous function of the information time in group sequential procedures for interim analyses. As inclusions can be fast during this pandemic or that data monitoring will be more complex than usual, it can be possible that interim analysis will not follow the initial plan. So, using a continuous function will allow to re-calculate the boundaries if necessary.
 
At each interim analysis, the Z statistics (for a difference of binary endpoints) is computed from the data of the two arms and will be compared to the efficacy and futility bounds.
 
If the value of Z is higher than the interim analysis specific upper bound (or lower than the lower bound), the trial is stopped for reasons of demonstrated efficacy (or futility); otherwise the trial will continue.
 
For interpretability, the plots and the results will be displayed on the maximum likelihood estimation (MLE) scale, but the final p-value will be computed using the log-odd-ratio normalized Z statistics. Analysis will be performed using R version 3.6.3 and the package gsDesign version 3.0-1.
 |

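### Interim and final tests ignore respiratory support at randomisation, a likely strong predictor of the endpoint; error rates hold, but power is lost and wrong futility stops are more frequent than they need be

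*SAP*

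**What the plan says.** The SAP's section on major changes defines the Day 21 endpoint: "failure corresponds to death or dependence from respiratory support, including mechanical ventilation or high-flow oxygen therapy". It justifies this choice partly by time on support: "diminishing the duration of respiratory support will permit to decrease ICU length-of-stay".

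The Sample Size section sets the planning rates: "The event rate is assumed to be 30% in the control group", and "an assumed event rate of 15% in the experimental group with 80% power". It gives "a one-sided Type I error rate of 2.5" (the percent sign is missing) and states that the design "requires sample size 290, for 6 interim analyses (5 during the trial and one final").

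The Statistical Analysis section says that at each interim analysis "the Z statistics (for a difference of binary endpoints) is computed from the data of the two arms" and is compared with the bounds, described as "a conservative O'Brien Fleming type of bound for superiority bound and a an aggressive bound for futility design". It bases the final p-value on a normalised log-odds-ratio Z. Neither statistic names a stratum or covariate.

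The SAP does not give the share of patients on support at entry, failure rates by baseline support, or the share of failures due to support rather than death. The protocol, which may stratify randomisation, is not at hand.

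**The concern.** For a patient ventilated at entry, success means surviving and being off support by Day 21. For a patient on less support, it means surviving without escalation, or coming off that support. These are different hurdles, so ventilation at randomisation is in effect a baseline measurement of one component of the endpoint. A test that ignores it leaves its variation in the noise.

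Two things make this matter here. First, the futility bound is meant to stop early, when numbers are small and chance differences in case mix are largest. Second, precision is hard to buy: the SAP reports about 290 therapeutic units, about 50 COVID-19 patients already included, no further placebo obtainable, and open-label continuation if more patients than units are needed.

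**Working it through.** **1. The plan's sample size.** With rates 0.30 and 0.15, one-sided 2.5% and 80% power, the unpooled fixed design needs (1.960 + 0.842)² × (0.30×0.70 + 0.15×0.85) / 0.15² = 7.85 × 0.3375 / 0.0225 ≈ 117.7 per arm, about 235 in all. The pooled-variance version needs 121 per arm.

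Six equally spaced looks, an O'Brien-Fleming-type or cubic power-family efficacy bound and linear, non-binding futility spending inflate this by 1.236 to 1.242. The result is 291 to 293 (unpooled) or 298 to 299 (pooled), close to the stated 290. The spending exponents and spacing are assumptions, as the SAP gives neither.

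**2. What stratifying does to the variance.** Assume half the patients are ventilated at entry, with control failure 45% if ventilated and 15% if not (30% overall) and the rates halved by treatment in each stratum.
- Crude: 0.30×0.70 + 0.15×0.85 = 0.3375.
- Within strata: ½[(0.45×0.55 + 0.225×0.775) + (0.15×0.85 + 0.075×0.925)] = 0.3094.
- Ratio: 0.3094 / 0.3375 = 0.917. Since 1/0.917 − 1 ≈ 9%, this is worth about 26 patients in 290. The gain is 1% for a 35/25 split, 4% for 40/20 and 17% for 50/10.

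**3. How large chance imbalance is.** At a first look of 290/6 ≈ 48 patients (24 per arm), the imbalance in the ventilated proportion has SD √(2×0.25/24) = 0.144, falling to 0.059 at 290. Under the design effect, its 95% contribution to the failure difference at that look is 1.96 × √((0.3375 − 0.3094)/24) ≈ 6.7 points. The total 95% range is ±1.96 × √(0.3375/24) = ±23.2 points crude and ±1.96 × √(0.3094/24) = ±22.3 points stratified.

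**4. Error rates.** In 60,000 simulated null trials using only a cubic power-family efficacy bound, one-sided type I error was 0.025 to 0.026 for the crude Z and 0.024 to 0.026 for the stratified Z, with failure 1 to 5 times as likely in patients on support. With both bounds active (O'Brien-Fleming-type efficacy, linear futility; 40,000 trials per scenario), false efficacy was 0.019 to 0.020 for both.

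**5. Power and wrong futility stops.** Same two bounds, 290 patients, overall rates 30% v 15%, a common odds ratio across strata, and a Cochran-Mantel-Haenszel Z as the stratified test:

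| On support at entry | Control failure by stratum | Power, crude → stratified | Early futility stop, crude → stratified |
|--|--|--|--|
| 50% | 30/30 | 79.9 → 79.7% | 16.7 → 16.9% |
| 50% | 40/20 | 79.7 → 80.9% | 17.1 → 16.0% |
| 50% | 45/15 | 79.3 → 82.5% | 17.3 → 14.7% |
| 50% | 50/10 | 79.5 → 85.0% | 17.2 → 12.7% |
| 80% | 34.6/11.5 | 79.6 → 80.5% | 17.0 → 16.1% |

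Results shift by a fraction of a point to about a point with how the treatment effect is spread over strata and with simulation error. Rounded over the runs made, power rises by about 1, 3 and 5 points in the 40/20, 45/15 and 50/10 rows, and wrong early futility stops fall by about 0.5 to 4.5 points. If support is not prognostic, the power loss is about 0.5 point or less.

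**6. What this means for one trial.** Take the 45/15 case under the design effect with the cubic efficacy bound. Among trials with an imbalance of at least 12.5 points at look 2, the chance of having stopped for futility by then is:

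| Excess of ventilated patients | Crude Z | Stratified Z |
|--|--|--|
| in the experimental arm | 13.3% | 6.3% |
| in the control arm | 2.5% | 6.4% |

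The crude rule thus depends on case mix about fivefold (13.3/2.5). The stratified rule does not.

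**The case against.** The strongest reply is that nothing is invalid. Under randomisation, chance imbalance in a prognostic factor is already part of the crude Z's null variance, the bounds perform as designed, and the crude test delivers the 80% power it was sized for. An unadjusted comparison of two proportions is a standard choice. All of this stands.

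A reader might still infer several stronger things that the SAP does not support:
- **That chance imbalance drives the stops.** Step 3 shows that stratifying narrows the early range by only about one point; most early noise is ordinary binomial variation. On the efficacy side the first bound is about 3.7 to 5.4. At 24 per arm even 3.7 needs a difference of about 3.7 × √(2×0.225×0.775/24) ≈ 45 points. The exposure is mainly on the futility side.
- **That half of the endpoint is support status.** Support is one of two components; its share of failures is not documented.
- **That imbalance can move the first-look difference by 8.5 of the planned 15 points.** That figure (1.96 × 0.144 × 0.30) holds only with no treatment effect. Under the design effect it is about 6.7.
- **That power rises from 87.5% to 90.1%.** Those are fixed-sample figures at 290, not those of the six-look design.

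Two further objections stand in part. Every stratum rate is assumed, so the gain could be close to nil. And the unseen protocol may stratify randomisation by baseline support; that would largely remove the imbalance, but the crude Z would then be conservative, so the stratified test would still be the right one.

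**Conclusion.** The point holds as one of efficiency and of the quality of the futility decision, not of validity. The SAP fixes unadjusted statistics at the interim looks and for the final p-value, although the endpoint itself points to an obvious baseline stratifier. The expected gain is about 1 to 5 points of power, with correspondingly fewer wrong futility stops, if half the patients are ventilated at entry and support is moderately to strongly prognostic. It is about 1 point if 80% are on support at entry with a threefold risk. These sizes rest on assumed stratum rates, assumed spending exponents and equally spaced looks, and the SAP itself says that looks may depart from plan. The direction does not depend on the exact values, provided support is prognostic.

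**What to change.** In the Statistical Analysis section, replace the crude interim Z and the unadjusted final log-odds-ratio Z by one statistic at all five interim analyses and the final one: a Cochran-Mantel-Haenszel score Z stratified on mechanical ventilation at randomisation (yes/no), compared with the same spending-function bounds. Keep the crude difference in failure rates as a supportive result. If the protocol stratifies randomisation by baseline support, use the same stratified test.

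The score form is preferable to a Mantel-Haenszel risk difference with an unpooled standard error. In the 45/15 case, the non-ventilated experimental stratum at the first look would hold about 12 patients with 12 × 0.075 = 0.9 expected failures, where an unpooled standard error is fragile; it also gave slightly higher false efficacy in simulation.

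Cost: a short change of SAP wording and one baseline variable that must be available at each look. The spending function and the 290 stay as they are. The downside is a power loss of about 0.5 point or less if ventilation at entry turns out not to be prognostic.

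### The final p-value is tied to a differently described Z from the one that stops the trial, and no reported p-value, estimate or interval that accounts for the six analyses is named (minor)

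*SAP*

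**What the plan says.** Under STATISTICAL ANALYSIS, the plan sets "a total of 6 analyses (5 interim analyses and a final" look, with Kim-DeMets spending and "a conservative O'Brien Fleming type of bound for superiority bound". For the decision, "the Z statistics (for a difference of binary endpoints) is computed from the data of the two arms" and compared with the efficacy and futility bounds. "If the value of Z is higher than the interim analysis specific upper bound", the trial stops for efficacy; below the lower bound it stops for futility.

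For reporting, results are "displayed on the maximum likelihood estimation (MLE) scale, but the final p-value will be computed using the log-odd-ratio normalized Z statistics". R and the gsDesign package are named as software.

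The SAP does not say whether the two Z statistics are one and the same, or which variance either uses. It does not say how the final p-value reflects the earlier looks. It names no confidence interval, adjusted or not, and no estimate other than the MLE.

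**The concern.** A spending function fixes when the trial may claim efficacy. It does not by itself define the p-value, effect size and interval that are then published, and those are what readers will use.

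Two things can come apart:

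- **The p-value and estimate.** An ordinary p-value ignores the chances to stop at earlier looks, so late in the trial it looks stronger than the sequential evidence. The MLE tends to overstate benefit when an early crossing ended the trial.
- **The Z statistic.** If the Z behind the p-value is not the Z that crossed, a trial can stop for efficacy and report a p-value whose own Z lies below the bound. Leaving the form open also allows a choice after a near-boundary result has been seen.

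**Working it through.** **Inputs from the SAP.** Failure 30% v 15%, one-sided alpha 2.5%, 80% power, 290 patients and six analyses (SAMPLE SIZE); O'Brien-Fleming-type efficacy bound (STATISTICAL ANALYSIS).

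**Assumptions, because the SAP gives no figures.** 1:1 allocation and six equally spaced looks. Efficacy spending is either Kim-DeMets with rho = 3, α(t) = 0.025·t³, or Lan-DeMets O'Brien-Fleming, α(t) = 2[1 − Φ(2.241/√t)]. Paired figures are in that order. There is no lower bound unless stated.

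**1. The plan's sample size.** A fixed design needs, per arm,

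[1.960·√(2·0.225·0.775) + 0.842·√(0.3·0.7 + 0.15·0.85)]² / 0.15² = 120.5, so 121 per arm and 242 in total.

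The stated 290 is an inflation of 290/242 = 1.20. The spending exponents are not given, so it cannot be verified. It is attainable: efficacy rho = 2 with futility rho = 1.5 gives 287, and rho = 4 with rho = 1 gives 298. Nothing below depends on it.

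**2. Efficacy bounds (recursive integration).**

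- rho = 3: 3.68, 3.14, 2.79, 2.51, 2.27, 2.06
- Lan-DeMets: 5.37, 3.71, 2.97, 2.54, 2.25, 2.04

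**3. P-value at the sixth look.** The ordinary one-sided p is 1 − Φ(z). The stage-wise p is the alpha spent over looks 1 to 5 plus the null probability of reaching look 6 and exceeding z there.

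- Spent by look 5: 0.025·(5/6)³ = 0.01447 / 0.01408.
- At z = 2.3: 0.01447 + 0.00402 = 0.01849 / 0.01408 + 0.00392 = 0.01800, about 0.018. The ordinary p is 0.011.
- At the final bound: 0.025 stage-wise by construction. The ordinary p is 0.0198 / 0.0204, about 0.020.

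If futility is obeyed (beta 0.20), the stage-wise values fall:

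| Assumed futility spending | At final bound | At z = 2.3 |
|---|---|---|
| rho = 1 | 0.0201 / 0.0199 | 0.0164 / 0.0159 |
| rho = 2 | 0.0226 / 0.0225 | 0.0177 / 0.0172 |

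The gap is mainly a late-look matter. At the look-3 bound with rho = 3, the ordinary p is 0.0026 and the stage-wise p is 0.025·(1/2)³ = 0.0031.

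**4. Estimate.** In 500,000 simulated trials at 30% v 15%, with looks at 24/48/72/97/121/145 per arm, the MLE averages 19.5 / 18.9 points after an early efficacy stop and 18.3 / 17.8 among all efficacy claims. The true difference is 15. Ordinary selection accounts for part of this: significant results of a fixed design average 16.1.

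Under a normal model (200,000 trials), the median-unbiased estimate lowers the mean among claims from 18.4 to 17.5 / 17.9 to 17.1. That is 0.9/3.4 and 0.8/2.9 of the excess, about a quarter. It exceeds the truth in 50% of all trials, against 58-59% for the MLE. A fixed-sample 95% interval has its lower limit above the truth in 3.4% / 3.8% of trials; the adjusted one in 2.5%.

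**5. Do the two Z statistics differ?** Take 22/72 v 8/72 failures at look 3. The difference is 0.1944, the pooled rate 0.2083 and the log odds ratio 1.258.

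| Form | Calculation | Z |
|---|---|---|
| Pooled difference | 0.1944/0.0677 | 2.87 |
| Log odds ratio, score | (22 − 15)/√5.9375 | 2.87 |
| Log odds ratio, Wald | 1.258/0.454 | 2.77 |
| Log odds ratio over its null standard error | 1.258/0.410 | 3.07 |

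Against the rho = 3 bound of 2.79, only the Wald form fails. Against the Lan-DeMets bound of 2.97, only the last form crosses.

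With the Wald form, 10.2% / 8.8% of difference-Z efficacy crossings have a log-odds-ratio Z below the same bound. None of these has a one-sided p above 0.021. In 96% / 93% of them the Wald Z crosses at another look. Overall efficacy crossing is 86.1% v 85.7% / 86.5% v 85.9%. The Wald share depends on a control rate for which the SAP writes "We choose to assume a 30% rate considering mortality or need of respiratory support for the control arm but this is uncertain": it is 1.7% / 1.5% of crossings at 50% v 35% and 17% / 14% at 20% v 10%. With the score form it is zero.

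**The case against.** **That two statistics are in use is not shown.** This stands. The log-odds-ratio phrase fits a score statistic, which equals the pooled difference Z, and the difference phrase may mean no more than a two-arm comparison. A reader might infer that the SAP prescribes two conflicting tests; the text supports only that the form is unspecified. The 9-10% figure belongs to the Wald form alone.

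**The count of looks is consistent.** This stands. A reader might see a conflict between "6 interim analyses (5 during the trial and one final" under SAMPLE SIZE and the count under STATISTICAL ANALYSIS. Both come to six, and SAMPLE SIZE includes the final analysis among them, so the boundary rule naturally covers the last look.

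**Type I error is not shown to be inflated.** This stands. One could suppose that the last look will be judged by an unadjusted p below 0.025 instead of the bound. The SAP states no such rule.

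**Futility is part of the plan.** This largely stands. Counting it nearly closes the p-value gap at the final bound, though not at Z = 2.3. Over all trials with rho = 1 futility the MLE averages 15.2 / 14.9, so the overstatement is conditional on stopping for efficacy.

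**The MLE may be only a display scale, and an unadjusted p-value is not stated outright.** This is fair, but no other p-value, estimate or interval is offered. Naming a spending function and a package defines bounds, not reported inference. The unseen protocol is a weak answer, because the SAP itself takes up how the p-value is computed.

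**Conclusion.** The point holds as a minor one about reported inference. The plan's boundary decisions are valid. What it leaves loose is the statistic behind the final p-value and any allowance for six looks in what is published.

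On the assumed O'Brien-Fleming-type spending, equal looks and 1:1 allocation, the ordinary p-value at the final bound is 0.020, against 0.025 stage-wise with no lower bound and 0.020-0.023 if futility is obeyed. At Z = 2.3 it is 0.011, against 0.018 and 0.016-0.018. After an early efficacy stop the MLE averages about 19 points for a true 15, part of which any significance filter would produce.

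Disagreement between the two Z statistics ranges from none (score form) to about 9-10% of efficacy crossings at the design rates (Wald form). Even then power is almost unchanged.

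**What to change.** Under STATISTICAL ANALYSIS:

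- Name the pooled difference Z as the statistic compared with the bounds at all six analyses, and as the basis of the final p-value. Remove the log-odds-ratio Z.
- Report a one-sided p-value by stage-wise ordering, with a median-unbiased estimate and the matching adjusted confidence interval for the risk difference. Other adjusted methods exist; this set is consistent with the difference Z.
- Keep the MLE for plots and description, labelled as unadjusted.

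The cost is a few sentences, a little more analysis code and slightly less favourable reported figures after an efficacy stop. The median-unbiased estimate will not remove all of the overstatement. The sample size does not change. The stopping rule also stays, since a difference Z is what the plan already compares with the bounds; the amendment only fixes its variance form, on which the SAP is silent.
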